## ***I. Study Protocol***

### **I.1. The purpose of the study (research objective)**

#### **Primary aim**

- Computer modelling of the lung deposition of aerosol drugs based on realistic individual breathing patterns to be measured within this study.\*

\* given that there are currently several innovative and generic products that are available for the treatment of patients with asthma and COPD, however not all products have the necessary data for computer modelling provided by companies or retrievable in the open literature, hence we are only modelling for products that have input data on drug aerodynamic characteristics.

#### **Secondary goals**

- Examination of the correlation between the lung deposition efficiency (the dose depositing in the lungs divided by the dose metered in the inhalation device) and the patients current health status.
- Evaluation of patients' inhalation device usage and suggestions for optimal usage according to the acquired breathing data and calculated lung deposition values.

### **I.2. Characteristics of patients to be included in the study (inclusion and exclusion criteria)**

#### **Inclusion criteria**

- diagnosed obstructive lung disease (asthma or COPD)
- proper usage of inhalation tool after being educated
- availability of whole body plethysmography measurement data from the last 6 months or the possibility to perform them before the start of the study (the most important parameter is reserve volume, RV)
- subject under outpatient/inpatient therapy
- over 18 years of age
- capable of acting and cooperating

#### **Exclusion criteria**

- the patient doesn't align with any of the criteria mentioned above
- the patient is incapable of filling out the questionnaire/questionnaires' parts that are accorded to him/her
- the patient doesn't agree to have data collected of him/her
- diagnosed heavy, not treated chronic illness
- not properly carried out /not evaluable lung function (spirometry) examination

### **I.3. Sampling and recruiting principles**

[figure not shown]
Every involved medical professional should opt for randomness in sampling. This includes the selection process but also the device order. We are involving examiners

for our test from different levels of healthcare servicing (university centre, regional institute, county hospital, panel clinic) aiming to ensure that the sampling venues (centrum related) to minimize centre specific effects.

Participation of patients is on a volunteer basis. Patient involvement in ambulant patient care occurs strictly in the time frame when the examination would take anyway place, no special visit (only for the study) will be needed. Only patients with proven records of COPD or asthma can be involved. In principle, in every centrum anyone who shows up for examination with asthma or COPD and is willing to cooperate can participate, given that it passes the inclusion criteria and no exclusion criterion applies to him/her. Children under 18 cannot be involved in the examination. There is no upper age constraint. There are no restrictions on gender or ethnicity. Minimum number of patients planned is 200.

#### **I.4. The examination**

Patient involvement will take place after the possibly emerging questions of the subject are answered and the patient is told about the whole goal of the examination and all of its details, has read and signed the leaflet and the patient-consent statement. After that the data of illnesses are obtainable according to the daily routine which are present suitably during the ambulant daily routine examination anyways.

The study not involving intervention in the care and treatment of patients consists of only one visit. Within this, as indicated on the data sheet, answers to questions in accordance with standard medical practice and individual respiratory function profile are recorded. The latter takes place only if the doctor has planned lung function measurement independently of the study.

#### **I.5. Actions to be undertaken during the visit**

The table below summarizes the data collection during the visit. The patients can only be involved and data can be registered only if these data would have anyway been obtained through a regular visit. In addition to the patient data, the centruns' data will be registered as well in the eCRF system, as complementary data helping the evaluation of the examination.

| Patients' data collection  | visit 1 (patient involvement) |
|---|--------------------------------------|
| Time  | 0 th day                  |
| Evaluation of the inclusion and exclusion criteria  | X                                    |
| Comprehensive informing of the patient  | X                                    |
| Signing of patient information leaflet and patient consent sheet  | X                                    |
| Recording of patient demographic data   | X                                    |
| Recording of the anamnesis  | X                                    |
| Recording of diagnostic   | X                                    |
| Recording of actual status  | X                                    |
| Smoking habit   | X                                    |
| Applied drug therapy, dose  | X                                    |
| Education on the use of inhalers  | X                                    |
| Whole body plethysmography measurement, only if it was not performed in the last 6 months (recording of RV and FVC) | X                                    |
| Recording of inhalation time and breath-holding time.   | X                                    |
| Registration of eventual side effects or unexpected events.   | X                                    |

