## **I.8. Data protection, publishing principles, IPD share plan**

The recorded personal information during the study is confidential. In all respects, the regulation of non-interventional examinations should be taken into account when collecting data (23/2002 EüM regulation), according to the year 2011. CXII. Law on the right to information self-determination, freedom of information, as well as the European Parliament and council (EU) 679/2016 General Data Protection Regulation.

The publication of the results of the study is likely to be useful information for pulmonologists, primary care workers, and also for specialists working in other fields, but its research value also manifests itself as research development potential. It can help to recognize the connections between the general condition of the patient, his drug use effectiveness, and the planning of later, prospective studies. It can also serve as a basis for more extensive studies. The head of the research shall decide on the preparation and publication of the communication on results as well as the naming of co-authors

In the case of an appropriate sample number (at least 30 patients per medicine and device) it is also possible to conduct interim analysis and publish the results of the study. Individual lung function results allow individual (personalized) modelling of drug deposition to be performed. The test can also be considered successful if statistically representative groups are not able to be formed. In this case, we perform modelling for individual measurements without aggregate results.

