## II. Statistical analysis plan

The data shall be processed and evaluated using statistical methods adopted in the case of tests not involving intervention.

Single-variable statistical methods: frequency (distribution), relative frequency, average, standard deviation, median, lower and upper quartiles. Multivariate regression analysis is used to analyse primary and secondary endpoints, if necessary.

The statistical analysis plan contains two parts, that is, the description of methods and tools for the processing of measured breathing parameters, and the description of methods and tools for the processing of the calculated deposited doses.

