### *II.1. Processing of the measured breathing data*

The analysis of the dependence of PIFdev for each selected device on patient demographic data (age, gender), anthropomorphic characteristics (height, weight), disease condition (expiratory volume at the end of the first second of forced exhalation: FEV1, forced vital capacity: FVC, Tiffeneau index: FEV1/FVC, GOLD grades) and baseline spirometric data characterizing the inhalation (peak inspiratory flow: PIF, inspiratory vital capacity: IVC, inhalation time: tin) is performed by an in-depth statistical evaluation of the interrelationships.

*Cross-correlation analysis* of the above parameters (except gender, and GOLD grades) in connection with each device is performed.

*Correlations* between different parameters are expressed by *Pearson coefficients*.

*Predictors* of PIFdev are looked for by stepwise *multiple regression analysis* using a backward elimination technique.

Mean PIFdev values of different patient subgroups upon gender, age, body mass index (BMI) and disease stages (GOLD grades) are analysed by conducting *two-sample t-tests*. Two age groups are formed. The cut-off age is 65 years. By the same token, two groups are formed upon BMI by using a cut-off value of 25 kg/m^2. Two groups are analysed also based on disease severity.

All statistical analyses are performed by the application of *OriginPro 2018* (version b9.5.0.193, OriginLab Corporation, Northampton, Massachusetts, USA) and *Minitab*® (version 18.1, Minitab, Inc., State College, Pennsylvania, USA) software packages. A value of  $p < 0.05$  is considered significant throughout the study.

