### *II.1. Processing of the computed lung deposition data*

An analysis of the correlation of the computed lung doses with the breathing parameters characterizing the inhalation through the selected devices (Q, tb-h, IV, tin, PIFdev) is performed. The strength of the correlation is expressed in terms of *Pearson coefficients* and any correlation is considered significant when  $p < 0.05$ .

In addition, the correlation of lung deposition with baseline spirometric breathing parameters expressing the breathing status of the patient (expiratory volume at the end of the first second of forced exhalation: FEV1, forced vital capacity: FVC, Tiffeneau index: FEV1/FVC, peak inhalation flow: PIF, peak expiratory flow PEF, inspiratory vital capacity: IVC) is studied. (PIF denotes the peak inhalation flow measured by standard spirometry, while PIFdev is the peak inhalation flow measured while inhaling through the device, PIFdev < PIF).

Mean values of lung doses characteristic of different age, gender and GOLD groups are analysed conducting *two-sample t-tests*. Two age groups are formed. The cutoff age is 65 years. Two groups are analysed also upon the classification of patients based on symptoms and exacerbation history.

All statistical analyses are performed by the application of *OriginPro 2018* (version b9.5.0.193, OriginLab Corporation, Northampton, Massachusetts, USA).

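### Does the regular-visit rule in I.5 shut out the through-device flow recording (PIFdev) that the SAP analyses?

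*Combined protocol and SAP*

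**What the plan says.** The protocol describes a single-visit, non-interventional study. Section I.5 restricts what may enter the database: "The patients can only be involved and data can be registered only if these data would have anyway been obtained through a regular visit". The table there summarises collection. Its only row on inhalation measures covers two times, inhalation and breath-hold. Section I.4 has a respiratory function profile recorded as indicated on a data sheet, with a condition: "The latter takes place only if the doctor has planned lung function measurement independently of the study".

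Other sections presuppose measurement through inhalers. The primary aim rests on "realistic individual breathing patterns to be measured within this study". Section I.3 asks for randomness and adds: "This includes the selection process but also the device order". Section I.6 says in general terms that the inputs needed for the modelling will be obtained.

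The SAP calls its first part "the description of methods and tools for the processing of measured breathing parameters". That part opens with "The analysis of the dependence of PIFdev for each selected device on patient demographic data". The section on computed lung deposition separates the two flows: "PIF denotes the peak inhalation flow measured by standard spirometry, while PIFdev is the peak inhalation flow measured while inhaling through the device". It lists five variables for the inhalation through the device: Q, tb-h, IV, tin and PIFdev. The section on measured breathing data, by contrast, lists tin with the baseline spirometric measures.

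**The concern.** The rule in I.5 carries no exception for measurements made for the study, and no section says that recording flow through an inhaler is part of a regular visit. Section I.4 ties the respiratory profile to planned lung function testing, and the SAP itself treats standard spirometry and through-device measurement as different things. A planned lung function test therefore does not imply a through-device recording.

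If the recording were not routine, a site following I.5 to the letter could not register the outcome of the first SAP part or the flow and volume correlates of the second. If it were routine at some centres only, the flow data would come from those centres alone, although I.3 recruits at four levels of care to limit centre effects. In addition, one symbol, tin, is classed as spirometric in one SAP section and as through-device in the other, and the table row does not say which it records.

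**Working it through.** The plan states no figure to reproduce. The check is a count, followed by a comparison of sections.

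**Count of table rows (I.5).** Leaving out the header and the time row, the activities are: criteria, informing, signing, demographics, history, diagnosis, current status, smoking, drug therapy, inhaler education, plethysmography (RV and FVC), inhalation and breath-holding time, and side effects. That is 13 rows. Rows naming an inhaled flow or an inhaled volume: 0.

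**Through-device variables without a named row.** The set is {Q, tb-h, IV, tin, PIFdev}, 5 in all. Breath-holding time always has a row. The documents do not say whether Q is recorded or derived, so both readings are shown.

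| Q | tin in the table row | Without a named row | Number |
|---|---|---|---|
| derived | through-device | PIFdev, IV | 2 |
| recorded | through-device | PIFdev, IV, Q | 3 |
| derived | spirometric | PIFdev, IV, tin | 3 |
| recorded | spirometric | PIFdev, IV, Q, tin | 4 |

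**Does absence from the table mean absence from the study?** The same test can be applied to the spirometric variables. FEV1, PIF, IVC and PEF are all analysed in the SAP, and I.2 excludes patients whose spirometry cannot be evaluated. None of the four has a named row. They must be carried by broad rows, such as diagnosis or current status, or by the data sheet cited in I.4, which is not part of the text available here. The same places could carry PIFdev and IV.

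**What does the inhalation row record?** Breath-holding time enters the analysis in one place only, as tb-h among the through-device variables. It is in neither list of spirometric measures. A row that pairs it with inhalation time is most naturally the inhalation through the device. A single flow-time recording of that inhalation gives peak flow, inhaled volume and inhalation time together.

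**Is the recording intended?** The primary aim has the patterns measured in the study, I.3 speaks of an order of devices, and I.6 expects the model inputs to be obtained. No section points the other way.

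**How strict is the rule?** Section I.3 says that outpatient involvement fits within the time of an examination taking place anyway, with no visit made only for the study. Read beside this, the I.5 sentence works as a bar on extra visits. The strictest reading would contradict the study's own primary aim.

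**Does the double use of tin affect a result?** Each SAP section says under which heading it uses tin, so an analyst can tell which quantity is meant. No planned analysis sets the tin results of one section against those of the other.

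**The case for a change.** The strongest reply is that the spirometry parallel proves only that the table is incomplete. Spirometry is ordinary care for these patients, whereas flow recording through an inhaler may not be. A field on the data sheet would show that PIFdev is collected, but not that a regular visit would have produced it, which is the test I.5 sets. On this view, the outcome of a whole SAP part deserves an explicit and permitted collection step.

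Part of this stands. The I.5 sentence is loosely worded, and no section states that the recording is routine. The consequence does not follow from that. Each step to lost data needs a premise the documents do not supply: that the recording is non-routine, or routine at some centres only, and that sites would apply the sentence against the declared aim.

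Nor can the harm be sized. No share of patients is given, so the permitted data could be anything from none to all of the planned minimum of 200, which is no estimate. The group size in I.8, "at least 30 patients per medicine and device", is 30/200 = 15% of that minimum, but it is a condition for an optional interim analysis. The same section accepts individual modelling without aggregate results if representative groups cannot be formed.

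**Conclusion.** No change to the plan follows. The observation is accurate: 0 of 13 rows name an inhaled flow or volume, and two to four of the five through-device variables have no row of their own. It is a gap in description, however, not a demonstrated bar on PIFdev. The purpose of the recording is plain from the aim, the sampling section and the SAP, and the existing inhalation row already points to the device manoeuvre. Investigators would record it and analysts would use it as defined. Writing this down would alter no variable, model or test. The double use of tin is a naming slip that each section's own heading resolves.

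The conclusion rests on two assumptions: that the data sheet or the broad table rows carry the flow and volume fields, and that sites read I.5 together with the aim and the no-extra-visit statement in I.3. Evidence that centres were declining to record PIFdev because of I.5 would reopen the question. The documents contain none.

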### **I.6. Beginning and duration of the examination**

The first patient can be involved if the Scientific Council for Health Scientific and Research Ethics Committee approves and afterwards the National Institute of Pharmacy and Food Health (OGYÉI) grants permission. In the first part of the study all the input data necessary for numerical modelling will be obtained.

Beginning date: 2022.08.01

End date: 2025.06.30

## **I.7. Legal background**

The legal frame is provided by:

- The European Commission 520/2012/EU implementing regulation (Annex II, paragraph 38), the 726/2004/EK Regulation of the European Parliament and of the Council and the 2001/83/EK implementation of pharmacovigilance activities provided for in the Directive of the European Parliament and of the Council
- XCV. law from 2005 on medicinal products for human use and amending other laws governing the pharmaceutical market
- CLIV. Law on Health Care from 1997
- 235/2009. (X. 20.) Government regulation of medical research in humans, clinical examination of test artefacts for human use, and on the regulations of enabling the use of medical tools intended to be used for clinical examinations in humans.
- 23/2002. (V. 9.) EüM Regulation on medical research on humans.
- 15/2012. (VIII. 22.) EMMI Regulation on pharmacovigilance of medicinal products for human use.

## **I.8. Data protection, publishing principles, IPD share plan**

The recorded personal information during the study is confidential. In all respects, the regulation of non-interventional examinations should be taken into account when collecting data (23/2002 EüM regulation), according to the year 2011. CXII. Law on the right to information self-determination, freedom of information, as well as the European Parliament and council (EU) 679/2016 General Data Protection Regulation.

The publication of the results of the study is likely to be useful information for pulmonologists, primary care workers, and also for specialists working in other fields, but its research value also manifests itself as research development potential. It can help to recognize the connections between the general condition of the patient, his drug use effectiveness, and the planning of later, prospective studies. It can also serve as a basis for more extensive studies. The head of the research shall decide on the preparation and publication of the communication on results as well as the naming of co-authors

In the case of an appropriate sample number (at least 30 patients per medicine and device) it is also possible to conduct interim analysis and publish the results of the study. Individual lung function results allow individual (personalized) modelling of drug deposition to be performed. The test can also be considered successful if statistically representative groups are not able to be formed. In this case, we perform modelling for individual measurements without aggregate results.

### *Individual Patient Data Share Plan*

The data sharing plan contains statements on the availability of individual participant data (including data dictionaries), information on what data in particular will be shared, what other documents will be available, when will data be available, with whom, for what type of analyses. In addition, the plan specifies the mechanism the data are to be made available.

According to the plan those IPD will be available that underlie the results published in research article(s) will be shared after deidentification.

The frame of IPD sharing is defined below:

Supporting information: Study Protocol

Time frame: Between months 9 and 36 after the publication of article(s).

Access criteria: IPD will be shared with investigators whose proposed use of the data has been approved by an independent review committee identified for this purpose. IPD will be shared to achieve aims in the approved proposal. Proposal may be submitted to [[contact]](mailto:[contact]).

URL: <https://data.mendeley.com>

### **I.9. Exploitation of results**

The research team (all experts included in this research) is looking forward to making the results public in the form of presentations in national and international congresses and publicizing it even if the series of measurements does not end with a positive result that can be evaluated for the endpoints. Moreover, if the results show that the deposition results based on individual breathing patterns and the aerodynamic characteristics of different drug particles differ significantly among each other, then they will be used in research aiming at the optimisation and personalization of inhaler choice and aerosol drug therapy.

### **I.10. Recording and reporting of side effects**

The head of research shall be responsible for reporting any undesirable drug effects detected by all researchers in connection with the study or in connection with the use of an inhaled medicine in connection with the study, and for complying with the relevant regulatory requirements in the field.

Experienced side effects are reported individually by the researchers towards OGYÉI, and they shall immediately be noted to the head of research and the sponsor. The fact of side effects is also recorded on the test sheets on a mandatory basis, which can be checked by the sponsor and the head of research.

The head of research takes responsibility to report the adverse reactions, side effects and other specific cases (hereinafter referred to collectively as "medicinal product safety information") experienced during the entire period of the non-interventional observational study and during the processing of the results as follows:

**Side effect (adverse drug reaction):** harmful and unwanted effects caused by medicines.

According to the perceptive doctor, the side effect may be causal to the use of the medicine. In addition to the harmful and unwanted effects resulting from the use under the marketing authorisation during the normal administration of medicinal products, adverse unwanted effects resulting from the pharmaceutical error and use not covered by the marketing authorisation shall also be considered as a side effect, including improper use and abuse of the medicinal product.

**Unexpected side effect:** a side effect which is not included in the prescription for use of the medicinal product or the frequency, nature, severity or outcome does not correspond to the side effect listed in the prescription for use.

**Serious side effect:** a side effect that endangers life, requires or prolongs hospitalization, causes permanent or significant damage to health, disability, congenital abnormalities, birth defects or death. It is medically significant, i.e. it does not meet any of the severity criteria listed above, but without intervention it leads to the appearance of one of the criteria.

**Special cases**, which shall also be reported to the sponsor if there are no side effects associated with the case:

- use of medicinal products during pregnancy
- use of medicinal products during breastfeeding
- overdose (either intentionally or accidental)
- ineffectiveness
- incorrect application
- medication error
- quality defect
- drug interactions
- paternal exposure
- misuse of medicinal products
- occupational harm to medicinal products
- transmission of an infectious agent by medicinal product
- off label (out-of-indication) drug application

The above-described information on the safety of medicines, whether or not there have been any side effects in connection with the specific case, or whether the side effect is well known or unexpected, or serious or not serious, shall be forwarded to the head of research and sponsor within 24 hours of the date on which the person concerned became aware. Study participants can also report side effects to the National Institute of Pharmacy through the contact details provided on the Institute's official website.

To avoid unnecessary administration and duplication, it is important that researchers report side effects only on one reporting route. The reports received by the head of research and sponsor will be forwarded/notified to the competent authorities in accordance with the legal requirements.

